1 PROTOCOL SUMMARY

1.1 Synopsis

Title of Study:

A Phase 4, Open-label, Randomized, Prospective, Interventional Post-authorization Efficacy and Safety Study of Mirabegron 50 mg and 25 mg for the Treatment of Overactive Bladder in Chinese Subjects

From approximately Q2/2020 to Q1/2023

Planned Total Number of Study Sites and Location(s):

Approximately 10-15 study sites in China

Study Objectives, Endpoints and Estimands:

Objectives and Endpoints:

The primary and secondary objectives and endpoints for this study are listed in the table below.

Objectives	Endpoints			
Primary				
• To evaluate the efficacy of mirabegron 50 mg for the treatment of OAB in Chinese subjects	• Change from baseline to the end of 12-week treatment period in mean number of micturition/24 hours			
Secondary				
• To evaluate the safety of mirabegron for the treatment of OAB in Chinese subjects	 Incidence and severity of AEs. Clinical laboratory tests (hematology, biochemistry and urinalysis) Vital signs (blood pressure and pulse) Routine 12-lead ECG Post Void Residual (PVR) 			
• To evaluate other efficacy variables of mirabegron 50 mg for the treatment of OAB	 Change from baseline to the end of 12-week treatment period in mean number of grade 3 or 4 (PPIUS) urgency episodes, incontinence episodes, urge incontinence episodes/24 hours and OABSS All efficacy variables change from baseline to weeks 4 and 8 			

- To explore mirabegron starting dose of 25 mg
- Change from baseline to weeks 4, 8, and 12 in mean number of micturition/24 hours, mean number of grade 3 or 4 (PPIUS) urgency episodes, incontinence episodes, urge incontinence episodes/24 hours and OABSS

AE: adverse event; NA: not applicable; OAB: overactive bladder; PPIUS: patient perception of intensity of urgency scale; OABSS: OAB Symptom Score.

Estimands

The estimand of most clinical importance for this study is defined by the following 4 attributes:

- Target population: all subjects who took at least 1 dose of the study drug, and in whom a nonmissing measurement for mean number of micturition per 24 hours at baseline and after administration of the study drug is available
- Outcome measurement: mean number of micturition per 24 hours prior to switching (if switching occurs)
 - Intercurrent events:
 - Dose escalation
- Population-based summary: change from baseline to week 12/end of treatment (EoT) in micturition frequency per day within dose groups

For this study, the treatment estimand is considered appropriate because of the fact that the response of subjects prior to switching is of primary interest. i.e., the estimate for 50 mg of mirabegron should be estimated from subjects who were randomized to 50 mg and the estimate for 25 mg should be estimated from subjects who were randomized to 25 mg while they were treated with 25 mg.

Study Population:

Male and female adult Chinese subjects (\geq 18 years of age) with overactive bladder (OAB; as defined according to the International Continence Society [ICS]).

Number of Subjects:

A total of 249 male and female Chinese subjects with OAB will be randomized into 2:1 ratio within 2 dose groups (50 mg of mirabegron and 25 mg of mirabegron).

Study Design Overview:

[figure not shown]
The study follows an open-label, randomized, 12-week, prospective, interventional postauthorization design for the treatment of OAB in approximately 249 Chinese subjects. Each subject will participate in one 12-week treatment period.

This study is designed to support the Imported Drug License (IDL) renewal and mirabegron safety surveillance in China. The data-cut with summaries and the planned primary analysis for the end of this study will be used for IDL renewal. Subjects fulfilling the screening inclusion/exclusion criteria will be randomized in 2:1 ratio to 50 mg mirabegron and 25 mg mirabegron using a computer-generated randomization to reduce selection bias. Treatments will be administered once daily orally recommended at the same time after meal during a 12-week, open-label treatment period. Study visits will take place at weeks 4, 8 and 12. For 25 mg mirabegron group, a dose escalation to 50 mg is permitted on visit 3 and visit 4 according to investigators' discretion.

Treatment Groups and Duration:					
Arm/IP Name	Mirabegron (BETMIGA®) Test product				
Use					
Dose	25 and 50 mg				
Frequency/Duration	Once daily doses for 12 weeks				
Route	Oral				
IP: investigational product					
The anticipated duration of the study for each subject, including screening and follow up, is approximately 16 weeks.					

1.2 Study Schema

Figure 1 Study Schema

QD: once daily.

[†]The investigators may want to assess if 25 mg dose is effective for this group. Subject to their discretions, a dose escalation to 50 mg is permitted on visit 3/week 4 or visit 4/week 8. [‡]Telephone contact or site visit.

1.3 Schedule of Assessments

Table 1Schedule of Assessments

	Screening Period		Treatment Period			Follow up period
Assessments	Visit 1	Visit 2 (Baseline)	Visit 3	Visit 4	Visit 5 (EoT) ⁹	Visit 6 (T/V ¹) or at Discontinuation of the Post treatment (End of Study) ^{11,12}
Week	-1 to -2	0	4	8	12	14
Visit Window (Days)	0	±2	±3	±3	±3	±3
Visit Number	1	2	3	4	5	6
Obtaining Informed Consent	Х					
Inclusion/Exclusion Criteria	Х	Х				
Medical History	Х					
Demographics	Х					
Physical Examination	Х				Х	
Randomization		Х				
Dispense/Collect IP		Х	Х	Х	Х	
Administration of IP ²		Х	←		→	
Issue Bladder e-diary	X ³	Х	Х	Х		
Retrieval of the Bladder e-diary		Х	Х	Х	Х	
OABSS ⁴		Х	Х	Х	Х	
Vital Signs ^{5,9}	Х	Х	Х	Х	Х	
Clinical Laboratory tests ^{6,9}	Х				Х	
Pregnancy Test ⁷	Х				Х	
Routine 12-lead ECG ^{8,9}	Х				Х	
PVR ¹⁰	Х				Х	
Previous and Concomitant Medication	Х	Х	Х	Х	Х	Х
AEs		Х	Х	Х	Х	Х

AE: adverse event; CRF: case report form; ECG: electrocardiogram; eCRF: electronic case report form; e-diary: electronic diary; EoT: end of treatment; IP: investigational product; PVR: post void residual; OAB: overactive bladder; OABSS: OAB Symptom Score.

Footnotes continued on next page

22 Mar 2021 Version 2.0

- 1. T/V = Telephone contact or site visit.
- 2. Daily IP administration will start on day 1 (i.e., the day on visit 2/week 0 [baseline]). For 25 mg mirabegron group, a dose escalation to 50 mg is allowable on visit 3 and visit 4 by investigator's discretion.
- 3. For the screening visit (visit 1/week -1 to -2 [screening]), all subjects will start with the completion of a 3-day bladder e-diary which includes collection of micturition volume over 2 days.
- 4. The OABSS questionnaire will be completed on visit 2/week 0 (baseline), visit 3/week 4, visit 4/week 8 and visit 5/week 12 (EoT).
- 5. Blood pressure, pulse measurements and body temperature will be measured in single measurements. Subject to be in the sitting position (when possible, otherwise supine, but always in the same position for each procedure). Subject should have been calm and without distress for at least 5 minutes. Preferably, the right arm should be used to measure vital signs. Body temperature will be measured with an ear thermometer. These measurements will be used to assess eligibility.
- 6. Hematology, biochemistry and urinalysis (urinalysis dipstick) tests will be performed at visit 1/week -1 to -2 (screening) and visit 5/week 12 (EoT). Refer to Table 8 for the list of clinical laboratory tests.
- 7. Urine pregnancy tests will be performed only in female subjects of childbearing potential at visit 1/week -1 to -2 (screening) and visit 5/week 12 (EoT) except for cases in which the possibility of pregnancy was clearly ruled out by hysterectomy, bilateral oophorectomy or the passage of 2 or more years after last menstruation.
- 8. Routine 12-lead ECGs will be taken after the subject has been resting in the supine position for at least 5 minutes. Routine 12-lead ECGs will be taken as single measurements.
- 9. The following sequence will be in effect when more than 1 assessment is required at a time point: routine 12-lead ECG, vital signs, and sampling for clinical laboratories.
- 10. PVR volume will be assessed using ultrasonography at visit 1/week -1 to -2 (screening) and visit 5/week 12 (EoT).
- 11. Subjects who withdraw early from the study after having received IP should complete both the EoT and end of study visits.
- 12. The end of study visit (visit 6/week 14 [end of study]) should take place at least 14 days after the EoT visit (visit 5/week 12 [EoT]).

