8.1 Discontinuation of Individual Subject(s) from Study Treatment

A discontinuation from treatment is defined as a subject who enrolled in the study and for whom study treatment is permanently discontinued for any reason.

The subject is free to withdraw from the study treatment and/or study for any reason and at any time without giving reason for doing so and without penalty or prejudice. The investigator is also free to discontinue the subject from study treatment or to terminate a subject's involvement in the study at any time if the subject's clinical condition warrants it.

The reason for discontinuation from study treatment must be documented in the subject's medical records.

A subject must discontinue study treatment for any of the following reasons:

- Subject requests to stop treatment
- Any clinical AEs, laboratory abnormality or intercurrent illness, in the opinion of the investigator, indicates continued treatment is not in the best interest of the subject
- If signs or symptoms of hypersensitivity to mirabegron are observed (e.g., anaphylactic reaction, erythema multiforme or exfoliative dermatitis)
- ALT or $AST > 8 \times ULN$
- ALT or $AST > 5 \times ULN$ for more than 2 weeks
- ALT or AST > 3 × ULN and TBL > 2 × ULN or international normalized ratio (INR)
 > 1.5 (if INR testing is applicable/evaluated)
- ALT or $AST > 3 \times ULN$ with the appearance of fatigue, nausea, vomiting, right upper quadrant pain or tenderness, fever, rash and/or eosinophilia (> 5%)

If a subject discontinues treatment prematurely, the subject will be encouraged to complete all scheduled visits to record all available information.

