8.2 Discontinuation of Individual Subject(s) from Study

All subjects who discontinue study treatment will remain in the study and must continue to be followed for protocol-specific follow-up procedures as outlined in Schedule of Assessments [Table 1]. The only exception to this is when the subject specifically withdraws

consent for any further contact with him/her or persons previously authorized by the subject to provide this information.

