### 5.4.5 12 Lead ECGs

A 12-lead ECG will be performed as single measurement at visit 1/screening and visit 5/week 12 (EoT). ECG traces will be evaluated by the investigator who will give an overall interpretation and may leave a qualifying comment in the eCRF. The overall interpretation will be recorded as:

- Normal, or
- Abnormal not clinically significant, or
- Abnormal clinically significant

As well as the overall interpretation, the following ECG variables will be supplied by the local laboratory: PR Interval (msec), RR Interval (msec), QRS Duration (msec), QT interval (msec) and Heart Rate (HR) (beats/min).

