For non-diary data, if a subject has more than one non-missing value within a visit window, the non-missing assessment which is closest to the target day within a window will be used. If two or more values are equally close and on different days, the latest non-missing value will be used. If two or more values are equally close and on the same day, the mean will be used for continuous variables or the worst observed case for categorical variables.

For diary data, the assessment date for the whole diary will be considered to be the date of the last valid day of the diary. If more than one diary has an assessment date within the same window, and if this results in more than one non-missing value of a diary variable, the non-missing value with the diary assessment day that is closest to the target day will be used. In case of ties on different days, the later non-missing value will be used. In case of ties located on the same side of the target day (i.e., more than one value for the same day), the mean of the values will be used for continuous variables and the worst value for categorical variables.

For analyzing diary data the labels of the study visits will not be used, they will be assigned based on the dates of assessment.

A two-day window around the visit date will be applied for the assignment of study period for exposure data.

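### A subject who stops mirabegron but stays in the study has ECG, laboratory and PVR values taken off drug, and the SAP tabulates them as Week 12 treatment-group results

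*Protocol*

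**What the plan says.** Protocol Table 1 schedules ECG, laboratory tests and PVR at Visit 1 and Visit 5 only. Visit 5 is placed at Week 12 with a window of 3 days either side and is labelled EoT. SAP Sections 5.4.3, 5.4.5 and 5.4.6 repeat this timing.

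Footnote 11 to Table 1 gives the one stated reason for an earlier EoT visit: "Subjects who withdraw early from the study after having received IP should complete both the EoT and end of study visits".

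Stopping the drug is handled as a different event. Protocol Section 8.2 states: "All subjects who discontinue study treatment will remain in the study and must continue to be followed for protocol-specific follow-up procedures". Section 8.1 adds that after premature discontinuation of treatment "the subject will be encouraged to complete all scheduled visits to record all available information". Neither section asks for a visit when the drug is stopped.

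In the SAP, Table 5 (Section 6.10.1) assigns ECG, laboratory and PVR values from Day 2 through Day 97 to Week 12, with a target of Day 84. If a window holds several values, "the non-missing assessment which is closest to the target day within a window will be used". A separate EoT row in Table 5 takes only values up to the last dose, in line with the EoT definition in the SAP's list of key terms. A footnote to Table 5 sends data from an Early Discontinuation visit to whichever window it falls in. The protocol defines no visit of that name.

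**The concern.** The schedule ties the only planned post-baseline ECG, laboratory and PVR readings to Week 12 or to leaving the study. Nothing ties them to the end of dosing. A subject who stops for an adverse event and stays, as the protocol asks, is therefore measured weeks after the last dose, when a drug effect may have resolved. The SAP then counts that reading as a Week 12 result of the treatment group.

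The tables concerned matter here. The study supports license renewal and safety surveillance, and QT prolongation and urinary retention are named adverse events of special interest (Protocol Section 7.3.6). ECG and PVR are the instruments that would show them. Mixing recovered values into Week 12 pulls any mean shift towards zero and can hide categorical changes.

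**Working it through.** The plan gives no figure on this point, so there is none to reproduce. The check is day arithmetic on the schedule, followed by tracing one subject through the SAP rules.

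**Inputs**
- Visit 5: Day 84, plus or minus 3 days, so Days 81 to 87 (Protocol Table 1; target day in SAP Table 5).
- Week 12 window for ECG, laboratory and PVR: Day 2 through Day 97. EoT row: up to the last dose (SAP Table 5).
- TEAE period: up to 30 days after the last dose (Protocol Section 9.4.3.1; SAP Section 5.4.1), used only for comparison.
- Day of last dose, L: an assumption, shown over a range.

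**Time off drug at Visit 5** = (84 ± 3) − L. **End of TEAE period** = L + 30.

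| Last dose (L) | Days off drug at Visit 5 | End of TEAE period |
|---|---|---|
| Day 14 | 67–73 | Day 44 |
| Day 28 | 53–59 | Day 58 |
| Day 56 | 25–31 | Day 86 |
| Day 70 | 11–17 | Day 100 |

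For a last dose on Day 28, the first scheduled post-baseline readings come on Days 81 to 87, well after the TEAE period closes on Day 58.

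**Which value becomes Week 12.** Days 81 to 87 lie inside Day 2 through Day 97, so the off-drug value qualifies. Suppose the subject also had an unscheduled on-drug ECG on Day 28. Its distance from target is 84 − 28 = 56 days, while a Visit 5 value is at most 3 days away, so Visit 5 is selected. In general an on-drug value lies at least 84 − L days from target. That exceeds 3 whenever L is before Day 81, so the off-drug Visit 5 value always wins for such a subject.

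**Where the value goes**
- Week 12 summaries and changes from baseline: included (SAP Sections 6.5.2, 6.5.4, 6.5.6.1).
- Laboratory and ECG shift tables, which run from baseline to Week 12: included (Sections 6.5.2, 6.5.4).
- QTcF categories and categorized QTcF changes, produced by visit: included (Section 6.5.4).
- EoT row: excluded, because Days 81 to 87 are later than Day 28. Without an unscheduled on-drug test, the subject has no EoT value.
- Liver categories: these use the highest value (Section 6.5.2.1), so a later recovered value cannot lower them.

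**Size of the dilution.** If a share p of Week 12 values is off drug, the effect in those subjects has fully resolved and nothing else drifts, a mean shift among subjects still on drug appears as (1 − p) of its size. The documents do not give p. As assumptions only: p = 0 gives 100%, p = 5% gives 95%, p = 10% gives 90%.

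**The case against.** The strongest reply is that the SAP already has an on-drug summary. The EoT result is limited to values up to the treatment stop date, and EoT summaries are specified for laboratory tests, ECG and PVR. This stands. A reader might infer that the plan has no on-drug safety summary for these measures, and that would be wrong. What the EoT row does not do is reach the shift tables, which are specified to Week 12, or supply a value for a subject who had no on-drug test.

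Second, other routes capture harm. Adverse events are collected at every visit, those of special interest are reported within 24 hours, abnormal laboratory results may be repeated, and a laboratory abnormality that prompts stopping has by definition been measured. This also stands. The readings are the only scheduled ones, not the only possible ones. But stopping the drug does not itself trigger any of these tests.

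Third, a Day 84 value is correctly labelled Week 12 by time. That is true of the label, but the tables are headed by treatment group and nothing marks which values are off drug.

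Fourth, a reader might infer that footnote 11 contradicts Sections 8.1 and 8.2. It does not: one covers leaving the study and the others cover stopping the drug and staying. What remains is ambiguity. Visit 5 is called EoT, so a site could reasonably hold it when dosing ends, and the SAP refers to an Early Discontinuation visit that the protocol never defines.

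**Conclusion.** The point holds for ECG, laboratory tests and PVR in the Week 12 summaries, the laboratory and ECG shift tables and the QTcF categories. For a subject whose last dose is Day 28 and who stays, the value entered is 53 to 59 days off drug. This assumes that sites follow the schedule as written and hold Visit 5 at Week 12. How much any table is diluted depends on how many subjects stop and stay, which the documents do not state and which may be few.

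Two stronger readings are not supported. A reader might take the 25% dropout in Protocol Section 9.2 as the share of Week 12 values that are off drug. That figure is dropout, and subjects who leave the study come under footnote 11, so it does not measure the stop-and-stay group. A reader might also extend the point to blood pressure and pulse. These are measured at Weeks 4, 8 and 12 and have their own EoT row, so a subject stopping at Week 4 already has a scheduled on-drug reading. Later off-drug readings can still enter the Week 8 and Week 12 columns, but vital signs are little affected.

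This is an inexpensive improvement to the safety tables. It does not bear on the primary efficacy analysis.

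**What to change.** 1. **SAP Table 5 and Sections 6.5.2, 6.5.4 and 6.5.6.1.** Using the last-dose date already collected (SAP Section 5.5.1), separate ECG, laboratory and PVR values taken after treatment stopped from the Week 12 treatment-group summaries, shift tables and QTcF categories, and tabulate them as post-treatment. State a short allowance after the last dose, fixed before hard lock, so that completers tested just after their final tablet are kept. Apply the closest-to-target rule only after this separation, so that an off-drug value cannot displace an on-drug one.

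2. **EoT trigger.** Footnote 11, Protocol Sections 8.1 and 8.2, and the SAP's Early Discontinuation visit must be reconciled on what triggers the EoT visit. Which trigger is right is for the sponsor and investigators to decide.

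**Cost.** Item 1 is one derivation plus additional table output, and SAP Section 1 allows revision before hard lock. The Week 12 columns will hold slightly fewer subjects and will describe those still on drug, so they should be read beside the post-treatment table. The change removes dilution but cannot recover on-drug events that were never measured. For item 2, a protocol amendment would need ethics approval (Protocol Section 10.1.1). SAP Appendix 9.1 describes the 249 subjects as already randomized, so a schedule change might reach few or none of them. Clarifying the term in the SAP remains possible.

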2 INTRODUCTION

The generic name of the investigational product (IP) is mirabegron sustained-release tablets (also called mirabegron oral controlled absorption system [OCAS] tablets internally) and the trade name is BETMIGA[®].

Mirabegron is a selective agonist for human beta 3-adrenoceptor (beta 3-AR). It is an approved chemical entity and first-in-class compound with a distinct mechanism of action compared to the current standard of care (primarily antimuscarinics).

Mirabegron is indicated for the symptomatic treatment of urgency, increased micturition frequency and/or urgency incontinence as may occur in adult patients with overactive bladder (OAB) syndrome.

In the mirabegron approval letter, China National Medical Products Administration (NMPA) requested further investigation into the usage (before/after meal) and dosage (including initiation dose) of mirabegron in Chinese patients and data should be submitted when the Imported Drug License (IDL) is renewed.

2.1 Study Rationale

In mirabegron approval letter, the NMPA has asked further data on the use of mirabegron in Chinese patients. The data ought to comprise mirabegron usage with two different starting doses available in China, 25mg and 50mg, as a prerequisite submission for the upcoming mirabegron IDL renewal.

This study will be an open-label, randomized, prospective, interventional post-authorized, oral dose once daily during 12-week period in male and female Chinese subjects with OAB. It is intended to determine the efficacy and safety of mirabegron with starting doses 50 mg and 25 mg for the treatment of OAB in Chinese subjects.

2.2 Background

OAB is a syndrome characterized by symptoms of urinary urgency with or without urge incontinence, often accompanied by frequency and nocturia in the absence of pathologic or metabolic factors that would explain these symptoms, according to the 2002 International Continence Society (ICS) definition [Neurourology and Urodynamics, 2019; Abrams et al, 2002, Charlson et al, 1987].

Several publications have studied the prevalence of OAB in developed countries. An overall OAB prevalence of 11.8% was observed in a population-based, cross-sectional survey of adults \geq 18 years of age in Canada, Germany, Italy, Sweden and the UK (the European Prospective Investigation into Cancer and Nutrition [EPIC] study). The prevalent rates of OAB were similar in men and women (10.8% versus 12.8%, respectively) and increased in individuals with age of > 40 years (13.1% in men and 14.6% in women, respectively) [Osman & Chapple, 2013; Irwin et al, 2006; Abrams et al, 2002]. A population-based survey of adults \geq 18 years of age in the US (the National Overactive Bladder Evaluation [NOBLE] 22 Mar 2021 Astellas Page 15 of 68 Version 2.0

study) reported an overall OAB prevalence of 16.5% with a similar distribution between the 2 sexes (16.0% in men and 16.9% in women).

The knowledge of the epidemiology of OAB is limited in Asia. A questionnaire-based survey conducted in randomly selected women 18 to > 70 years of age, who were treated at the outpatient clinics for nonurologic or nongynecologic problems under the supervision of medically trained personnel in 11 Asian countries (China, Hong Kong, India, Indonesia, Malaysia, Pakistan, Philippines, Singapore, South Korea, Taiwan and Thailand), reported an overall OAB prevalence of 53.1%, with only 21.1% wanting treatment [Lapitan & Chye, 2001]. In the same 11 Asian countries, a prevalence of 29.9% was reported in a self-administered questionnaire survey completed by a randomly chosen sample of male patients (18 to \geq 70 years of age) visiting clinics other than urology clinics [Moorthy et al, 2004]. An internet-based self-administered survey conducted among men and women at least 40 years of age in China, Taiwan and South Korea reported an OAB prevalence of 20.8% (19.5% in men and 22.1% in women) and increased significantly with age, from 10.8% in those 40 to 44 years of age to 27.9% in those > 60 years of age (p = 0.001) [Chuang et al, 2019]. An overall OAB prevalence of 26.5% in adults 30 years of age and older (18.0% in men and 28.7% in women) was reported in another population-based, cross-sectional questionnaire survey conducted in South China [Chen and Li, 2016].

Many studies have shown significantly greater symptom bother, worse health-related quality of life (HRQoL), higher rates of depression and decreased enjoyment of sexual activity in OAB patients [Chen & Li, 2016; Osman & Chapple, 2013; Coyne et al, 2008; Stewart et al, 2003]. In addition, the economic burden of OAB is substantial.

The management of OAB is multimodal, including lifestyle modifications, behavioral therapies and pharmacological therapeutic strategies. Antimuscarinics, which exert their effect through the blockade of postjunctional muscarinic receptors, are currently the mainstay of pharmacological treatment of OAB and they represent the most commonly prescribed drugs. Meta-analyses of several randomized controlled trials (RCTs) have shown that antimuscarinics (including propiverine, fesoterodine, tolterodine, oxybutynin, solifenacin, trospium and darifenacin) are efficacious, safe and well-tolerated therapies that improve HRQoL [Chapple et al, 2008; Novara et al, 2008]. However, the lack of persistence with antimuscarinics is a well-known challenge in OAB treatment, which may occur due to the side-effects such as dry mouth, conspiration, blurred vision and urinary retention or the lack of perceived efficacy [Andersson, 2013]. A systematic literature review indicated high rates of discontinuation from 12-week RCTs, ranging from 4% to 31% in treatment groups and 5% to 20% in placebo groups, respectively. Findings from medical claims data also suggested that over half of the patients never refilled their initial prescription and that adherence levels were low, with mean/median medication possession ratio (MPR) values ranging from 0.30 to 0.83 [Sexton et al, 2011].

Mirabegron, a first in class beta-3-adrenergic receptor agonist, has been approved for OAB treatment in the US, Europe, Canada, Japan, Australia, Hong Kong, Korea, China and Taiwan. A review of 6 RCTs of mirabegron concluded that mirabegron had clinically

significant efficacy and tolerability in treating OAB symptoms. The tolerability profile of mirabegron provided the potential for improving patient adherence with OAB treatment, as dry mouth was often the reason for antimuscarinics treatment discontinuation [Chapple et al, 2014].

